3.1. EVALUATION OF THE ANTICIPATED RISK/BENEFIT RATIO

Colistimethate sodium (commercially available as Promixin[®]/Tadim[®]) is indicated for the management of chronic pulmonary infections due to *P. aeruginosa* in adult and paediatric patients with CF.

Colistimethate sodium has a well-established safety profile in subjects with CF (Promixin[®] Summary of Product Characteristics [SmPC] [18]).

Patient exposure data for CF patients in key European markets using commercial colistimethate sodium drug product (Promixin[®]/Tadim[®]) delivered with the CCI nebulizer estimates the number of treatment days as 13,146,075 (March 2003 to 31st July 2017, inclusive), with a low level of spontaneous adverse drug reactions reported.

Common side-effects of nebulisation include coughing and bronchospasm with the first administration, observed in approximately 10% of subjects. Other common side effects on the respiratory system include chest tightness and bronchoconstriction.

During the trial, subjects will administer an inhaled short-acting bronchodilator (e.g. salbutamol/albuterol) provided by the Sponsor prior to each IMP administration in order to reduce the side-effects described above. If subjects prefer not to use the bronchodilator and tolerate IMP without it this is acceptable. To monitor subjects for bronchial hyperreactivity in response to inhaled colistimethate sodium which may develop with continued use, regular spirometric examinations are included in the trial schedule.

Further side-effects observed include hypersensitivity reactions such as skin rash and cases of sore throat or sore mouth (also potentially due to superinfection with *Candida* species).

High serum concentrations may lead to a reduction of pre-synaptic acetylcholine release and thus may prolong the effects of muscle relaxants and increase fatigue. In addition, high serum concentration may result in renal impairment; whilst this is highly unlikely during inhalation therapy, in the current protocol an evaluation of renal function will be performed at baseline and during treatment.

Colistimethate sodium should be used with extreme caution in subjects with porphyria.

It is anticipated that administration of colistimethate sodium, administered twice daily via the CCI for 12 months, may significantly reduce the frequency of pulmonary exacerbations compared to placebo in subjects with NCFB chronically infected with *P. aeruginosa*. Anticipated benefits to the subject randomised to colistimethate sodium include improved lung function and overall CCI

4. OBJECTIVES

The primary objective of the trial is to investigate the effect of the use of inhaled colistimethate sodium, administered twice daily via the CCI for 12 months, compared to placebo in subjects with NCFB chronically infected with *P. aeruginosa* on the frequency of pulmonary exacerbations.

The secondary objectives of the trial are to investigate the effect of the use of inhaled colistimethate sodium, administered twice daily via the CCI for 12 months, compared to placebo in subjects with NCFB chronically infected with *P. aeruginosa* on:

- CCI [REDACTED]
- [REDACTED]
- [REDACTED]
- [REDACTED]
- [REDACTED]
- [REDACTED]
- [REDACTED]
- [REDACTED]

All the trial variables are described in [Section 18.2](#).

5. ETHICS REQUIREMENTS

This trial will be conducted in compliance with last version of Declaration of Helsinki; refer to the link <https://www.wma.net/policies-post/wma-declaration-of-helsinki-ethical-principles-for-medical-research-involving-human-subjects/>, with International Council for Harmonisation (ICH) Good Clinical Practice (GCP), in particular E6(R2), with the applicable regulatory requirements and with Zambon and contract research organisation (CRO) standard operating procedures (SOPs).

6. DESIGN AND DURATION OF THE CLINICAL TRIAL

6.1. CLINICAL TRIAL DESIGN

This is a randomised, multi-centre, double-blind, placebo-controlled, parallel-group interventional trial in subjects with NCFB suffering from chronic infections with *P. aeruginosa*.

The trial will be conducted in approximately 100 sites in 15 estimated countries.

Please refer to [Appendix 1](#) for a trial flow chart.

The study will consist of a total of 7 clinic visits (see [Section 8](#)) with a follow-up phone call two weeks after discontinuation of treatment. Additional clinic visits, where feasible, and weekly phone calls will be conducted following pulmonary exacerbations (or any episodes

of pneumonia) until resolution, and a clinic visit may also be required during a pulmonary exacerbation or pneumonia ([Section 8.8](#)).

At Screening (Visit 1), subjects will be asked to provide Informed Consent prior to any trial related assessment and will be checked against inclusion and exclusion criteria. Their medical history will be recorded. Additionally, subjects will undergo 12-lead ECG, laboratory assessments and will provide sputum samples. These results will be available before Visit 2; if the Screening Visit sputum sample is negative for *P. aeruginosa*, up to two further samples may be collected and tested, within 30 days, after which, if all three are negative, the subject will be asked not to attend Visit 2 and will be deemed a Screen Failure (see [Section 8.1](#)).

However, should the Investigator deem it preferable to repeat screening, the subject can be re-screened once within 2 months after Visit 1. In this case the subject must re-consent to participate and all screening assessments must be performed again.

At Visit 2 (within 30 days after Visit 1), eligible subjects with *P. aeruginosa* cultured from their screening visit sputum sample will be randomised in a 1:1 ratio to receive either colistimethate sodium or placebo.

It is planned to enrol 210 subjects into each treatment group.

It is planned that subjects will attend for a further 5 visits at the sites at 1, 3, 6, 9, and 12 months after Randomization (visit 2) (i.e. Visits 3, 4, 5, 6, and 7) and will have 1 follow-up phone call at 12.5 months.

Procedures performed at all clinical visits are detailed in [Section 8.0](#) and will include documentation of concomitant medications and treatment emergent adverse events (TEAEs) as well as spirometry to determine forced expiratory volume in 1 second (FEV₁) and forced vital capacity (FVC). Additionally, the subjects will be asked by the Investigator for information on any NCFB pulmonary exacerbations that were not reported.

Further sputum samples will be collected at Visits 2, 3, 5 and 7, to be analysed CCI [REDACTED]. Sputum samples collected at Screening (Visit 1) and at the end of treatment (Visit 7) will have isolates retained by the central laboratory for later analysis CCI [REDACTED].

At Visits 2, and at each post-baseline study visit, [REDACTED] will be assessed using the CCI [REDACTED].

In case subjects feel that they are experiencing a NCFB pulmonary exacerbation (as defined in [Section 18.2](#)), they should contact the investigational site immediately to discuss their symptoms and, if feasible, to arrange an Exacerbation Visit (which should take place within 2 working days of the exacerbation starting, if possible). The Investigator will check whether the pulmonary exacerbation meets the criteria defined in this Clinical Trial Protocol (CTP), will decide on an appropriate course of action (including systemic antibiotic treatment, if required) and will perform the assessments defined in the [Section 8.8](#).

6.2. DURATION OF CLINICAL TRIAL

The overall study duration (from first patient first visit to last patient last visit) is expected to be from Q2 2017 to Q4 2020.

The maximum expected duration of participation in this trial for an individual subject, from Visit 1 (Screening) to the follow-up phone call is 13.5 months. Treatment duration will be 12 months.

The start of the trial is defined as first subject in, i.e. Visit 1 for the first subject.

The end of the trial is defined as the last subject out, i.e. when the last subject had the follow-up phone call. The end of the trial for the purposes of the primary statistical analysis is defined as the last subject completing the trial.

If the trial is prematurely stopped, please refer to [Section 15](#).

7. CLINICAL TRIAL POPULATION

7.1. NUMBER OF SUBJECTS

A total of 420 subjects (210 in each treatment group) are planned to be enrolled into the trial. The enrolment is competitive among sites.

For a description of sample size calculation, please refer to [Section 18.3](#).

7.2. SELECTION OF SUBJECTS

7.2.1. INCLUSION CRITERIA

Subjects can be included in the trial if they meet all the inclusion criteria listed below:

- 1) are able and willing to give informed consent, following a detailed explanation of participation in the protocol and signed consent obtained;
- 2) are aged 18 years or older of either gender;
- 3) are diagnosed with NCFB by computerised tomography (CT) or high resolution CT (HRCT) as recorded in the subject's notes and this is their predominant condition being treated;
- 4) had at least 2 NCFB pulmonary exacerbations requiring oral or inhaled antibiotics or 1 NCFB pulmonary exacerbation requiring intravenous antibiotics in the 12 months preceding the Screening Visit (Visit 1) and had no NCFB pulmonary exacerbation with or without treatment during the period between Visit 1 and Visit 2;
- 5) have a documented history of *P. aeruginosa* infection;
- 6) are clinically stable and have not required a change in pulmonary treatment for at least 30 days before the Screening Visit (Visit 1);
- 7) have pre-bronchodilator FEV₁ \geq 25% of predicted;
- 8) had a positive sputum culture for *P. aeruginosa* from an adequate sample taken at the Screening Visit (Visit 1) or during the screening period.

7.2.2. EXCLUSION CRITERIA

Subjects are not eligible for the trial if they meet one or more of the exclusion criteria listed below:

- 1) known bronchiectasis as a consequence of cystic fibrosis (CF);
- 2) known history of hypogammaglobulinaemia requiring treatment with immunoglobulin, unless fully replaced and considered immuno-competent by the Investigator;
- 3) myasthenia gravis or porphyria;
- 4) severe cardiovascular disease such as severe uncontrolled hypertension, ischaemic heart disease or cardiac arrhythmia and any other conditions that would confound the evaluation of safety, in the opinion of the Investigator;

- 5) had major surgery in the 3 months prior to the Screening Visit (Visit 1) or planned inpatient major surgery during the study period;
- 6) receiving treatment for allergic bronchopulmonary aspergillosis (ABPA);
- 7) had massive haemoptysis (greater than or equal to 300 mL or requiring blood transfusion) in the preceding 4 weeks before the Screening Visit (Visit 1) or between Visit 1 and Visit 2;
- 8) respiratory failure that would compromise patient safety or confound the evaluation of safety or efficacy of the study in the opinion of the Investigator;
- 9) current active malignancy, except for basal cell carcinoma or squamous cell carcinoma of the skin without metastases;
- 10) taking immunosuppressive medications (such as azathioprine, cyclosporine, tacrolimus, sirolimus, mycophenolate, rituximab), and/or anti-cytokine medications (such as anti-IL-6 and anti-tumour alpha necrosis factor products) in the preceding year before the Screening Visit (Visit 1);
- 11) known history of human immunodeficiency virus (HIV);
- 12) current treatment for non-tuberculous mycobacterium (NTM) lung disease or tuberculosis.
- 13) known or suspected to be allergic or unable to tolerate colistimethate sodium (intravenous or inhaled) or other polymyxins, including previous evidence of bronchial hyper-reactivity following inhaled colistimethate sodium;
- 14) treatment with long term (≥ 30 days) prednisone at a dose greater than 15 mg a day (or equivalent dose of any other corticosteroid) within six months of the Screening Visit (Visit 1);
- 15) new maintenance treatment with any oral macrolides (e.g. azithromycin/erythromycin/clarithromycin) started within 30 days of the Screening Visit (Visit 1) and between Visit 1 and Visit 2;
- 16) use of any intravenous or intramuscular or oral or inhaled anti-pseudomonal antibiotic (except chronic oral macrolide treatment with a stable dose) within 30 days prior to the Screening Visit (Visit 1) and between Visit 1 and Visit 2;
- 17) pregnant or breast feeding or plan to become pregnant over the next year or of child-bearing potential and unwilling to use a reliable method of contraception for at least one month before randomisation and throughout their involvement in the trial;
- 18) significant abnormality in clinical evaluations and/or laboratory tests (physical examination, vital signs, haematology, clinical chemistry, clinically relevant impaired renal function, defined as serum creatinine levels ≥ 2.0 x upper limit of normal, ECG) endangering the safe participation of the patient in the study at the Screening Visit (Visit 1) and during the study;
- 19) participated in another investigational, interventional trial within 30 days prior to the Screening Visit (Visit 1);
- 20) in the opinion of the Investigator not suitable for inclusion for whatever reason.

Contraceptive methods

Safety in human pregnancy has not been established. Animal studies do not indicate a teratogenic potential. However, there is evidence that colistimethate sodium crosses the placenta and, consequently, there is potential for foetal toxicity if administered during pregnancy. Colistimethate sodium should only be given during pregnancy if the benefits outweigh any potential risk.

Female subjects can be enrolled if they are either post-menopausal for at least 2 years, or surgically sterilized or have undergone hysterectomy.

Female subjects of child-bearing potential must be willing to avoid pregnancy. They are required to have a negative pregnancy test at inclusion (see [Section 9.1.4](#)), and should use highly effective methods of birth control for 1 month prior to randomisation, throughout the trial duration and up to 1 month after the last dose of IMP, which include:

- combined (oestrogen and progestogen containing) hormonal contraception associated with inhibition of ovulation (oral, intravaginal or transdermal)
- progestogen-only hormonal contraception associated with inhibition of ovulation (oral, injectable or implantable)
- intrauterine device
- intrauterine hormone-releasing system
- surgical sterilization (e.g. bilateral tubal ligation or occlusion)
- male sterilization (vasectomised partner)
- sexual abstinence.

Throughout the course of the study male participants with female partners of child-bearing potential must abstain from sexual intercourse, use condoms or use effective contraceptive precautions. Male participants must also not take part in the donation of sperm whilst enrolled on the study.

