 5. had major surgery in the 3 months prior to the Screening Visit (Visit 1) or planned inpatient major surgery during the study period;
 6. receiving treatment for allergic bronchopulmonary aspergillosis (ABPA);
 7. had massive haemoptysis (greater than or equal to 300 mL or requiring blood transfusion) in the preceding 4 weeks before the Screening Visit (Visit 1) or between Visit 1 and Visit 2;
 8. respiratory failure that would compromise patient safety or confound the evaluation of safety or efficacy of the study in the opinion of the Investigator;
 9. current active malignancy, except for basal cell carcinoma or squamous cell carcinoma of the skin without metastases;
 10. taking immunosuppressive medications (such as azathioprine, cyclosporine, tacrolimus, sirolimus, mycophenolate, rituximab), and/or anti-cytokine medications (such as anti-IL-6 and anti-tumour alpha necrosis factor products) in the preceding year before the Screening Visit (Visit 1);
 11. known history of human immunodeficiency virus (HIV);
 12. current treatment for non-tuberculous mycobacterial (NTM) lung disease or tuberculosis;
 13. known or suspected to be allergic or unable to tolerate colistimethate sodium (intravenous or inhaled) or other polymyxins, including previous evidence of bronchial hyper-reactivity following inhaled colistimethate sodium;
-

-
14. treatment with long term (≥ 30 days) prednisone at a dose greater than 15 mg a day (or equivalent dose of any other corticosteroid) within 6 months of the Screening Visit 1 (Visit 1);
 15. new maintenance treatment with any oral macrolides (e.g. azithromycin/erythromycin/clarithromycin) started within 30 days of the Screening Visit (Visit 1) or started between Visit 1 and Visit 2;
 16. use of any intravenous or intramuscular or oral or inhaled anti-pseudomonal antibiotic (except chronic oral macrolide treatment with a stable dose) within 30 days prior to the Screening Visit (Visit 1) and between Visit 1 and Visit 2;
 17. pregnant or breast feeding or plan to become pregnant over the next year or of child-bearing potential and unwilling to use a reliable method of contraception for at least one month before randomisation and throughout their involvement in the trial;

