8.6. FOLLOW-UP PHONE CALL (2 WEEKS ± 3 DAYS AFTER END OF TREATMENT)

A follow-up phone call will be performed at 2 weeks ± 3 days after the discontinuation of IMP.

The following procedures will be performed during the call:

- documentation of concomitant medications;
- AE monitoring.

If the result of the susceptibility test at the end of treatment (Visit 7) suggests the subject is resistant to colistin, he/she will be called for an extra visit with sputum collection for analysis of CCI [REDACTED].

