16.8.1. REPORTING SERIOUS ADVERSE EVENTS

Investigators must report SAEs **within 24 hours of first becoming aware of the event**.

The SAE must be reported through the eCRF to the CRO's Pharmacovigilance group as given in the contact details provided in the "List of Zambon/CRO personnel" at the beginning of this CTP.

If there is any issue with the electronic reporting process, such as internet failure or database issues, this must not delay SAE reporting. The back-up procedure is to send the back-up paper SAE Form to the CRO's Pharmacovigilance group by email or fax using the following contact details:

Email: CCI [REDACTED]
Fax: CCI [REDACTED]

Note: Any reports submitted on paper must be retrospectively added to the eCRF as soon as possible.

The community standards of confidentiality must always be maintained and any relevant national legislation on data protection must be followed.

SAEs are reportable from the time a subject signs the informed consent to the follow-up phone call 2 weeks after the last dose of IMP.

If the Investigator becomes aware of any SAE occurring to a subject within the follow-up window established in this CTP, he/she will report the SAE as above. The SAE will be also reported in the eCRF.

If the Investigator becomes aware of any SAE outside the follow-up window established in this CTP, it is the Investigator's responsibility to report the SAE to the CRO. The Investigator might use the eCRF, as described above. However, the SAE is not an event which occurred within the trial period.

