16.10. PREGNANCY

Subjects must be instructed that known or suspected pregnancy occurring during the trial should be confirmed and reported to the Investigator, who must then withdraw the subject from the trial without delay. This also applies in case the partner of a male subject becomes pregnant at any time during the whole course of the study (in this event a specific ICF for the subject's partner will be obtained).

In the event that a subject is subsequently found to be pregnant after inclusion in the trial, then the subject will be withdrawn from the study and the pregnancy will be actively followed up to term and the status of mother and child will be reported by the Investigator to the CRO through the appropriate pregnancy report provided by the CRO.

The Investigator will send pregnancy reports within the timeframes of SAEs.

If pregnancy results in an abnormal outcome that the Investigator and/or the Sponsor considers to be due to the IMP, this will be treated as an expedited ADR report.

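### Protocol 7.2.2 gives two contraception standards and end dates for the same women, and about half of the longer post-dose month has no scheduled contact or explicit pregnancy-reporting rule

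*Protocol*

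**What the plan says.** **Two contraception requirements.** Exclusion criterion 17 (Protocol 7.2.2) excludes women of child-bearing potential who will not use a reliable method "for at least one month before randomisation and throughout their involvement in the trial". The Summary repeats this: "unwilling to use a reliable method of contraception for at least one month before randomisation and throughout their involvement in the trial". Further down in 7.2.2, the contraceptive-methods text requires highly effective methods for the month before randomisation, then "throughout the trial duration and up to 1 month after the last dose of IMP". The paragraph on male participants gives no post-dose period: "Throughout the course of the study male participants with female partners of child-bearing potential must abstain from sexual intercourse" or use one of the listed alternatives.

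**Foetal risk.** The same text says that the drug crosses the placenta and that "there is potential for foetal toxicity if administered during pregnancy". It also says that animal studies do not suggest teratogenicity and that safety in human pregnancy is not established.

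**End of follow-up.** Protocol 8.6: "A follow-up phone call will be performed at 2 weeks ± 3 days after the discontinuation of IMP". Its listed content is concomitant medications and adverse events. Section 6.2 counts individual participation from screening to this call, 13.5 months at most.

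**Pregnancy testing and reporting.** Sections 8.5 and 9.1.4 and the Appendix 1 flow chart place the last dipstick at Visit 7, the visit at which the last supervised dose is given. Section 16.10 says that "known or suspected pregnancy occurring during the trial should be confirmed and reported to the Investigator". Section 16.8.1 says: "SAEs are reportable from the time a subject signs the informed consent to the follow-up phone call 2 weeks after the last dose of IMP".

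**The concern.** A woman willing to use contraception only until the phone call passes criterion 17 but does not meet the contraceptive-methods text. A site reading one passage could advise her differently from a site reading the other, on both the method and the stopping date.

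Pregnancy capture also stops before the longer contraception period does. The most relevant case is a conception in the last days of dosing. It falls within 16.10, but a dipstick on the day of the last dose is unlikely to detect it, and the call two weeks later has no pregnancy question. A conception after the call but within the contraception month is not clearly covered by 16.10. Because the protocol says that safety in human pregnancy is not established, each such outcome has safety value, and what is at stake is how completely those outcomes are captured.

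**Working it through.** **Inputs**
- Screening up to 30 days, treatment 12 months (365.25 days), call 14 ± 3 days after the last dose: Protocol 6.2, 8.1 and 8.6.
- Contraception to 1 month after the last dose: Protocol 7.2.2, contraceptive methods.
- The protocol does not give the length of 1 month in days. I assume 28 to 31, with an average month of 365.25/12 = 30.44 days.

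**Step 1. Reproduce the plan's own figures.**
- Maximum participation: (30 + 365.25 + 14) / 30.44 = 13.45 months; the plan states 13.5.
- Timing of the call after randomisation: (365.25 + 14) / 30.44 = 12.46 months; the plan states 12.5.

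Both agree, so a subject's involvement does end at the call.

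**Step 2. Compare the two end dates.**
- Criterion 17: about 12.5 months after randomisation.
- Contraceptive-methods text: (365.25 + 30.44) / 30.44 = 13.0 months.
- Difference: 30.44 − 14 = 16.4 days, a little over two weeks.

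**Step 3. Share of the post-dose month after the last scheduled contact**, (month − call day) / month:

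| Call day | 28-day month | 30-day month | 31-day month |
|---|---|---|---|
| 11 | 17 d (61%) | 19 d (63%) | 20 d (65%) |
| 14 | 14 d (50%) | 16 d (53%) | 17 d (55%) |
| 17 | 11 d (39%) | 13 d (43%) | 14 d (45%) |

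The nominal range is 50% to 55%; the full range is 39% to 65%.

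**Step 4. What each mechanism covers after the last dose.**

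| Mechanism | Day 0 to the call | Call to 1 month |
|---|---|---|
| Scheduled pregnancy test | None after Visit 7 | None |
| Scheduled contact | One call, no pregnancy question listed | None |
| Pregnancy reporting (16.10) | Covered as during the trial | Not stated |
| Routine SAE reporting (16.8.1) | Covered | Only if the investigator learns of the event |

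The two-week split applies to contact and to explicit reporting. For testing, the whole post-dose month is uncovered.

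**The case against.** **The two texts can be read together.** Criterion 17 tests willingness at entry, and the contraceptive-methods text adds operational detail. A woman who follows the longer text also satisfies the criterion, and nothing tells anyone to stop early. This is fair and lowers the practical risk. It does not remove the difference in wording: the criterion, taken alone, sets a lower standard and an earlier end.

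**A reader might infer that half of a foetal-risk window goes unobserved.** The documents do not support that. The protocol ties potential toxicity to dosing during pregnancy, gives no reason for the 1 month, and defines no post-dose risk period. The month is a contraception requirement, and the percentages above count calendar days without scheduled contact, not missed pregnancies.

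**A reader might also infer that such pregnancies escape every reporting rule.** That is wrong too. A conception around the last doses occurs during the trial and so falls under 16.10. A congenital anomaly is an SAE (16.4.1), and 16.8.1 makes the investigator responsible for reporting SAEs learned of after the window. Section 16.10 makes an abnormal outcome attributed to the study drug an expedited report, with no time limit. These routes are passive, however. Pregnancy itself is not in the SAE definition, and the 16.10 provision for a subject later found to be pregnant calls for withdrawal, which presupposes that she is still in the study.

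**Other material may fill the gap.** The consent form and the CRO's pregnancy report form are not among the documents reviewed and could carry later instructions. That limits any claim that outcomes would be lost, but it does not reconcile the protocol's own passages.

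**Conclusion.** The point holds as an internal inconsistency with a modest gap in safety capture. Section 7.2.2 sets two standards and two end dates, about two weeks apart, for the same women. About half of the longer post-dose month (50% to 55% nominally, 39% to 65% at the extremes) has no scheduled contact and no explicit pregnancy-reporting rule, and no pregnancy test is scheduled in any of it. Passive reporting of later serious events remains.

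This rests on three assumptions: a month is 28 to 31 days; involvement in the trial means up to the follow-up call, as 6.2 implies; and a same-day dipstick is unlikely to detect a conception in the last days of dosing, which is general reasoning rather than a figure in the documents. That few subjects are affected is also an assumption, since no age distribution is given. Sample size, power, type I error and the efficacy analyses are unaffected. This is a low-priority correction.

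**What to change.** 1. Reconcile criterion 17, in both the Summary and 7.2.2, with the contraceptive-methods text so that one standard and one end date apply. Which standard and date to use is for the sponsor to decide. Check the paragraph on male participants, and the partner-pregnancy wording in 16.10, against the same decision.
2. State in 16.10 that pregnancy reporting runs to that same date, keeping the existing SAE timeframe for site reports.
3. Add to the existing follow-up call in 8.6 a question about pregnancy and a reminder to report one up to that date.

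The cost is a minor protocol edit and a line or two in the call script. No extra visit or test is needed, and the statistical analysis does not change.
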